## 10. SUBJECT DISCONTINUATION

The removal of a study subject by the Principal Investigator could occur due to the following reasons:

1. Adverse Event
2. Concomitant treatments or illnesses incompatible with the study
3. Withdrawal of consent by the participant
  - a. All subjects will be informed of the fact that they may, of their own free will, withdraw their consent to participate in the study, if they so wish.
4. Lost to follow-up
5. Emergence of a non-inclusion criterion
6. Researchers' decision
7. Protocol violation

Those subjects who, for some reason, are discontinued from the study will not be replaced. Data from these subjects will not be analyzed unless the reason for their discontinuation was related to the investigational product.

The Investigator should carefully track and document all premature discontinuations and the reasons on study documentation and also, when necessary, on the "adverse event" form.

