An aliquot of the test article will be placed in a reservoir. The UniTest PC device will be dipped into the reservoir and then pricked into volar forearm skin of panelist/subject. A new skin prick device will be used for each prick and will be performed in identical order for each panelist/subject. The UniTest PC device will be pressed through the drop of allergen extract and held against the skin for at least 1 second. There will be equal pressure applied for each test. The epithelial layer of the skin will be penetrated without inducing bleeding. A new UniTest PC device will be utilized for each allergen.

Excess solution from drops will be blotted using a clean Kim-wipe tissue. A timer will be used, sites will be read at 15-20 minutes following application.

Positive and negative controls will be measured first. The negative control should exclude presence of an allergen reaction. The positive control should include presence of an allergen reaction. Both controls must show correct reaction in order to proceed with study.\*

\*Erythema present in the test site of the negative control: According to the consulting allergist, it is acceptable for the negative control to elicit an allergic response as long as the wheal diameter of the positive control exceeds the wheal size of the negative control by at least 3mm. This is to account for individuals who have sensitive skin.

The test sites will be visually evaluated for any reaction by an allergist. The allergist will be blinded to any previous scores the entire study. A trained ALS staff member will scribe for the allergist. Subjects will be brought into the same

sufficiently lit (fluorescent bulbs) room each visit. Subjects will be sitting and will be instructed to expose test site. Grading will be performed during daylight hours between 8am-5pm

The wheal of each test will be measured. A positive being a wheal of  $\geq 3$  mm. (Section 7. Experimental Techniques and Methods).

Subjects will be given a panelist instruction handout. Subjects will be dismissed with instructions to keep the test area dry and to not expose the test area to direct sunlight. Subjects will also be instructed not to wet, wipe, cleanse, or cover the test sites. Subjects will be instructed to notify clinical staff during the course of the study should they begin using any new medications, cease taking any medications or have any change in their medical condition. Subjects will be instructed to remain in the testing facility.

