At approximately 6-hour ( $\pm 30$  minutes) following the skin prick, test sites will be evaluated by an allergist. The allergist will be blinded to any previous scores. Subjects will be brought into the same sufficiently lit (fluorescent bulbs) room each visit. Subjects will be sitting and will be instructed to expose test site. Grading will be performed during daylight hours between 8am-5pm.

Following the 6-hour grading, subject will be dismissed from the testing facility and instructed to return approximately 24-48 hours post-application. Subjects will also be instructed not to wet, wipe, cleanse, and cover the test sites.

At approximately 24-48 hours following the skin prick, test sites will be evaluated by the allergist. The allergist will be blinded to any previous scores. Subjects will be brought into the same sufficiently lit (fluorescent bulbs) room each visit. Subjects will be standing and will be instructed to expose test site. Grading will be performed during daylight hours between 8am-5pm.

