## **14. STATISTICAL RATIONALE AND DATA REPORTING**

Evaluation of results consists of only one physiological measure (that of wheal/flare) measured at 3 time points: T1=15 minutes after SPT, T2=6hr after SPT and T3=24-48 hrs. after SPT. Our power analysis calculation indicates at a confidence level of 99% and confidence interval of 1.35, we will need a sample size of n=20. No statistical analysis will be performed. No significant effect or interaction effects are anticipated hence the small sample size. Skin responses to the test product and controls for each subject will be presented in a table in the final report.

Product reporting for skin sensitization will be based on statistically significant positive scores at each interval. Any subject that has erythema present in the negative control eliciting an allergic response will be included as long as the wheal diameter of the positive control exceeds the wheal size of the negative control by at least 3mm. This is to account for individuals who have sensitive skin. This data will be noted in the clinical findings.

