**Initials/Date**

**APPENDIX II:**

**23-233 A QUESTIONNAIRE FOR SUBJECT ENROLLMENT**

**Subject ID:** \_\_\_\_\_

**Subject Initials:** \_\_\_\_\_

1) Are you aware that this study involves research? **YES / NO** (circle one)

2) How long is your study participation? \_\_\_\_\_

3) Where will the test product be applied? \_\_\_\_\_

4) How many test sites will be used? \_\_\_\_\_

5) Female volunteers:

Are you pregnant, or nursing or planning to get pregnant? YES / NO / MALE (circle one)

If of child bearing potential, list means of birth control subject agrees to use while participating on study.

\_\_\_\_\_

6) What are some possible side reactions expected from this study? \_\_\_\_\_

7) How many total visits will you make to the facility? \_\_\_\_\_

8) What is the expected duration of the testing visits? \_\_\_\_\_

9) Do you understand the study will require a use of a UniTest PC device on the test sites, which may be painful for individuals?

**YES / NO** (circle one)

10) Do you understand that you will be discontinued from the study without full compensation if you fail to complete all required study visits?

**YES / NO** (circle one)

11) Have all your questions about the study process been answered? **YES / NO** (circle one)

**L:** \_\_\_\_\_ **b\*** \_\_\_\_\_ **Fitzpatrick Score:** \_\_\_\_\_ (I-V)

ALS Staff Initial \_\_\_\_\_ Date \_\_\_\_\_

Subject Initial \_\_\_\_\_ Date \_\_\_\_\_

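### Section 10 can drop valid 15-minute and 6-hour readings from product reporting when a subject later leaves for a reason unrelated to the product

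*Combined protocol and SAP*

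**What the plan says.** Section 10 lists reasons for removing a subject, among them loss to follow-up, withdrawal of consent and protocol violation. It says that such subjects are not replaced, and then: "Data from these subjects will not be analyzed unless the reason for their discontinuation was related to the investigational product". The unit of exclusion is the subject. Readings taken before the subject left are not treated separately.

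Appendix II asks each subject at enrollment: "Do you understand that you will be discontinued from the study without full compensation if you fail to complete all required study visits".

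Section 14 sets readings at 15 minutes, 6 hours and 24-48 hours. It states "No statistical analysis will be performed", then "Skin responses to the test product and controls for each subject will be presented in a table in the final report", and then "Product reporting for skin sensitization will be based on statistically significant positive scores at each interval". It names no analysis set and gives no rule for subjects with partial data.

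On the timing of visits, Section 9.6 says: "Following the 6-hour grading, subject will be dismissed from the testing facility and instructed to return approximately 24-48 hours post-application". For the time before that grading it says: "Subjects will be instructed to remain in the testing facility". The same paragraph also speaks of dismissing subjects with instructions, so those two statements need reconciling.

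Sections 5 and 7 plan for about 30 subjects enrolled and at least 20 completing.

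**The concern.** A wheal at 15 minutes is evidence about the 15-minute interval whether or not the subject comes back a day or two later. Section 10 decides whether that reading is used by asking why the subject left, not whether the reading was sound. Because reporting is per interval, nothing in Section 14 requires a complete set of three readings before the first two can be used.

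In a study of 20 to 30 subjects, one subject can separate a result with no positives from a result with one. If that subject is excluded because of a later missed visit, evidence that bears directly on the objective in Section 2 is lost, although it was already in hand. If the excluded readings are negative, the loss is of precision only.

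**Working it through.** **1. The plan's own figures.** Section 14 gives n = 20 from a 99% confidence level and an interval of 1.35. With n = (z·SD/E)², the SD, the unit of 1.35 and whether it is a half or full width are all missing, so n = 20 cannot be reproduced. Solving backwards with two-sided z = 2.576, SD = E·√20/z. That is 1.35 × 4.472/2.576 = 2.34 if 1.35 is the half-width, or 0.675 × 4.472/2.576 = 1.17 if it is the full width. Nothing below depends on this. Enrolling 30 so that 20 complete leaves room for 30 − 20 = 10 losses (10/30 = 33.3%). That is a ceiling inferred from the two numbers, not a stated dropout rate.

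**2. One subject traced through the text.**
- At 15 minutes the controls are checked and the test site is read (Section 9.6).
- At 6 hours the site is read again, and the subject then leaves the facility (Section 9.6).
- The subject does not return at 24-48 hours and is discontinued (Appendix II; loss to follow-up is also a listed reason in Section 10).
- The reason is not product-related, so the subject's data are not analyzed (Section 10).
- Product reporting at 15 minutes and 6 hours (Section 14) can therefore omit two valid readings.

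**3. Illustration: the excluded subject is the only positive.** Assume 21 subjects with valid 15-minute readings, one positive, and that subject excluded. Limits are one-sided 95% Clopper-Pearson, a convention chosen here because the plan defines none.
- All valid readings kept: 1/21 = 4.8%; upper limit, the 0.95 quantile of Beta(2, 20), is 20.7%.
- Section 10 applied: 0/20 = 0%; upper limit 1 − 0.05^(1/20) = 13.9%.

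**4. Illustration: no positives at all.** The upper limit is 1 − 0.05^(1/n).
- n = 20: 13.9%
- n = 25 (five more valid subjects kept, an assumption): 11.3%
- n = 30 (ceiling): 9.5%

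At one-sided 99%, 0/20 would give 1 − 0.01^(1/20) = 20.6%. The size of the limit depends on the convention; that it narrows when more readings are kept does not.

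**5. Chance that a single positive is excluded if dropout is random.** With k later dropouts among 20 + k subjects with valid readings, the chance is k/(20 + k).
- k = 1: 1/21 = 4.8%
- k = 5: 5/25 = 20%
- k = 10: 10/30 = 33%, a ceiling, since control failures and losses before the prick may use part of the 10.

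**6. Bias check under random dropout.** With 1 positive in 25 and 5 random dropouts, the expected rate among completers is (1 − 5/25) × 1/20 = 0.80 × 0.05 = 4.0%, the same as 1/25. Random loss does not bias the rate.

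**7. Direction otherwise.** It is not fixed. Dropping positives lowers the observed rate and dropping negatives raises it.

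**The case against.** The strongest reply is that the rule may have little practical effect. Section 14 plans no statistical analysis and promises a table covering each subject. On that reading a discontinued subject's wheal is still visible in a short listing, and being left out of the analysis is not the same as being left out of the report. This stands in part: the sections can be read together as listing everyone but not evaluating the discontinued. But the table is not said to include discontinued subjects, and a listing would not by itself count the reading. Per-interval product reporting is the only evaluation planned, so it is the natural object of the Section 10 rule.

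Second, Section 10 keeps subjects who leave because of the product, adverse events still go to the sponsor (Section 11), and reasons for discontinuation are documented. All true, and it narrows the gap to a reading followed by an unrelated departure. None of it returns such a reading to product reporting.

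Third, some exclusions are justified, for example when an interfering medication has compromised a reading. That is right, but the rule does not separate those readings from sound ones.

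A reader might also infer that the lack of blinding lets the relatedness judgement be steered. Section 7 does describe a study without blinding, and Section 9.6 offers only this: "The allergist will be blinded to any previous scores the entire study". But every subject receives the same product and both controls, so blinding to assignment would not change how a missed visit is classed. The documents also do not say who judges whether a discontinuation is related. The point does not rest on this.

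**Conclusion.** The point holds as a defect in a stated rule. Section 10 can remove valid 15-minute and 6-hour readings, including a positive wheal, because of a later departure unrelated to the product, and a missed last visit is an ordinary way for this to happen. Sections 10 and 14 do not settle whether such readings are at least listed.

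Confidence is high on what the rule says. The effect on the study's conclusion cannot be quantified: there is no expected number of such losses and no study-level decision rule, since Section 14 refers to statistical significance while planning no analysis. The rates, limits and probabilities above are illustrations under assumed counts and carry no weight beyond that.

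A reader might infer that the rule biases the positive rate downward, or that a third of the data will be lost. The documents support neither. Random dropout leaves the expected rate unchanged, the direction of any non-random effect is not fixed, and 10 of 30 is only a ceiling.

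The change should be made: the loss is avoidable because the readings have already been taken.

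**What to change.** Replace the quoted sentence in Section 10 with:

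> Every subject who is pricked and meets the control criterion at the initial reading is counted at each time point with a recorded reading, whatever the reason for later discontinuation, to the extent consent allows. A reading is left uncounted only if it was technically compromised (for example by interfering medication, or by a protocol violation affecting the test site before that reading), as decided and documented without knowledge of the test-product result; it is still listed and flagged. An eligibility criterion discovered after the prick does not by itself remove a reading; such subjects are counted and flagged, and a result without them may be shown as supportive.

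The last sentence matters here. The dressing contains fish-derived collagen (Section 4) and known fish allergy is an exclusion (Section 5.2), so a positive wheal must not become uncountable because an allergy comes to light afterwards. The control criterion is tied to the initial reading because Section 9.6 states no control check at the later ones.

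In Section 14, state that the per-subject table includes discontinued subjects with the reason for and time of discontinuation, and give the number of subjects read at each time point.

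Cost: denominators that differ by time point, slightly more tabulation, and a protocol amendment approved by the client and the testing facility and submitted to the IRB (Section 12). No additional data are collected.

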## 11. ADVERSE EVENTS

The most commonly observed reactions in this study are:

1. Itching, redness, rash, peeling, swelling and in rare cases blistering.
2. There is also a possibility of a reaction from the tape, which may result in hyperpigmentation.

There also may be risks and discomforts, which are not yet known.

An adverse event (AE) is any unfavorable medical occurrence experienced by the subject, whether or not the event may be related to the test article.

Each adverse event must be promptly recorded and sufficiently documented by the Study Director in the source documentation and case report form even if the adverse event is assessed by the Study Director as unlikely to be related to the study. Adverse events are graded on a scale of severity (mild, moderate, severe, or life threatening) and

on a scale of relationship to the product (unknown, unrelated, unlikely, possible, probable, or definite). All adverse events will be reported to the Sponsor within five business days. All adverse events will be followed up until resolved, stabilized, the subject is lost to follow-up or the event is otherwise explained. All follow-up information should be reported to the Sponsor.

A serious adverse event (SAE) as defined in the CFR 312.32 is "any experience that is fatal or life threatening, is permanently disabling, requires inpatient hospitalization, or is a congenital anomaly, cancer, or overdose". All serious adverse events will be reported to the Sponsor within 24 hours of ALS Beauty & Personal Care notification.

If, according to the Investigator, medical care is warranted, appropriate referrals will be made. ALS Beauty & Personal Care will follow adverse events until resolution.

## **12. PROTOCOL AMENDMENT**

Any changes to the study protocol will be approved in writing by the client and ALS then submitted to the IRB for approval prior to implementation in the study, unless immediate change is necessary to eliminate hazard to the subject(s). Any violations in the study conduct will be documented as protocol deviations. Protocol amendments will be signed by the Investigator and Sponsor representative.

## **13. STUDY REPORT**

A final report will be issued to the sponsor within 4 weeks of study completion.

## **14. STATISTICAL RATIONALE AND DATA REPORTING**

Evaluation of results consists of only one physiological measure (that of wheal/flare) measured at 3 time points: T1=15 minutes after SPT, T2=6hr after SPT and T3=24-48 hrs. after SPT. Our power analysis calculation indicates at a confidence level of 99% and confidence interval of 1.35, we will need a sample size of n=20. No statistical analysis will be performed. No significant effect or interaction effects are anticipated hence the small sample size. Skin responses to the test product and controls for each subject will be presented in a table in the final report.

Product reporting for skin sensitization will be based on statistically significant positive scores at each interval. Any subject that has erythema present in the negative control eliciting an allergic response will be included as long as the wheal diameter of the positive control exceeds the wheal size of the negative control by at least 3mm. This is to account for individuals who have sensitive skin. This data will be noted in the clinical findings.

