## 7. EXPERIMENTAL TECHNIQUES AND METHODS

This will be a single center, with no randomization or blinding, study design in 30 healthy adult subjects, age 18-70 years. Based on prior experience approximately 30 subjects will be enrolled to ensure 20 subjects complete the study.

Skin response to the test product and both positive and negative controls will be evaluated and measured by an allergist. If the measured diameter is  $\geq 3$ mm in response to the test product with expected reactions to both the positive and negative controls, the site will be considered a positive allergen.

Initial reading will take place after 15 minutes looking for the presence or absence of a wheal and flare at all three sites and measuring the diameter of both the wheal and flare if present. The wheal at the positive control must exceed a wheal at the negative control by 3 mm. A second reading is conducted about 6 hours after the SPT administration and similar measurements are taken. The subjects return to the office 1-2 days after the initial administration for a third test reading and measurements. A positive reaction is present when there is a measurable wheal of  $>3$  mm. Small wheals are confirmed by palpation. The skin prick reaction is quantified by measuring the mean diameter of the wheal, using a ruler marked in mm. If the result is a circular wheal, one measurement of the diameter (in mm) is sufficient; if ovoid or irregular, two diameters are measured (smallest and largest) and the numbers are added and divided by 2 (mean diameter). A flare alone is measured but is not of any clinical significance. The flare, area of erythema, may also be recorded by the same method.

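### Section 14 rules out statistical analysis yet rests the product conclusion on statistical significance, and its n=20 cannot be reproduced from the inputs it gives

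*Combined protocol and SAP*

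**What the plan says.** Section 14 makes four statements that bear on this point.

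- Endpoint: "Evaluation of results consists of only one physiological measure (that of wheal/flare) measured at 3 time points", at 15 minutes (T1), 6 hours (T2) and 24 to 48 hours (T3).
- Sample size: "Our power analysis calculation indicates at a confidence level of 99% and confidence interval of 1.35, we will need a sample size of n=20". It then adds: "No significant effect or interaction effects are anticipated hence the small sample size".
- Analysis: "No statistical analysis will be performed". Each subject's responses to the product and the controls will be tabulated in the final report.
- Reporting rule: "Product reporting for skin sensitization will be based on statistically significant positive scores at each interval".

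Section 7 works at the level of the single site. A test-product diameter of at least 3 mm, "with expected reactions to both the positive and negative controls, the site will be considered a positive allergen". Later in the same section, "A positive reaction is present when there is a measurable wheal of" more than 3 mm. The control criterion is: "The wheal at the positive control must exceed a wheal at the negative control by 3 mm". Sections 5 and 7 plan about 30 enrolled so that at least 20 complete.

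**The concern.** The reporting rule is the only sentence that says how individual readings become a statement about the product. It calls for statistical significance in a section that excludes statistical analysis. If both sentences stay, either no product conclusion can be drawn, or a test has to be chosen once the data are known. Several subjects who are individually positive under section 7 could then be summarised as not significant.

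The sample-size sentence has a related weakness. It is called a power analysis, but it names neither a power nor an alternative, and the 1.35 has no unit. The further argument, that no effect is expected and so a small sample will do, leaves out what a reader of a negative result needs: how large a positive rate the study could have missed.

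**Working it through.** **1. The two sentences on analysis.** Significance needs a test, a comparator and a level, and with three readings it also needs a statement on multiplicity. Section 14 gives none of these. Section 7 and section 9.6 define a positive site and a valid control, not a test. The two sentences cannot both be followed.

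**2. Does the choice of test matter?** One illustration, with tests and background rate assumed by me. Suppose 4 of 20 subjects are positive to the product and none to the negative control.

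- Paired exact test against the negative control, one-sided: p = 0.5^4 = 0.0625, not significant at 5%.
- One-sample exact binomial test against an assumed 5% background: P(X ≥ 4 | n = 20, p = 0.05) = 0.0159, significant at 5%.

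The same four reactions support opposite product statements.

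**3. Reproducing n=20.** The inputs in section 14 are a 99% confidence level and 1.35. The unit, SD or rate, power, sidedness and width convention are missing there and everywhere else. No formula returns 20 from these two numbers alone, so I solved for the missing input. The natural unit is mm, because the section names wheal/flare as the only measure and section 7 measures it in mm.

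For a mean with two-sided 99% confidence and half-width h, n = (q × SD / h)², so SD = h × √20 / q. Here q = 2.576 (z) or 2.861 (t on 19 df).

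| Meaning of 1.35 | h (mm) | SD giving n=20, z | SD giving n=20, t |
|---|---|---|---|
| half-width | 1.35 | 1.35 × 4.472 / 2.576 = 2.34 mm | 1.35 × 4.472 / 2.861 = 2.11 mm |
| full width | 0.675 | 1.17 mm | 1.06 mm |

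The answer depends heavily on the missing SD. With 1.35 as half-width, assumed SDs of 1, 2 and 3 mm need n = 4, 15 and 33 by z (8, 19 and 37 by t). With 1.35 as full width, SDs of 1 and 2 mm need 15 and 59 by z (19 and 63 by t). The plan also estimates no mean wheal, so on this reading the calculation would size a quantity that is never reported.

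**4. What a result with no positives can show.** With 0 of n positive, the exact one-sided upper limit for the positive rate is 1 − a^(1/n), where a is 1 minus the confidence level.

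| Evaluable subjects | one-sided 95% | one-sided 99% |
|---|---|---|
| 20 | 1 − 0.05^(1/20) = 13.9% | 1 − 0.01^(1/20) = 20.6% |
| 30 | 1 − 0.05^(1/30) = 9.5% | 1 − 0.01^(1/30) = 14.2% |

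These limits depend on the number of subjects and not on whether an effect was expected. The sentence beginning "No significant effect or interaction effects are anticipated hence the small sample size" is therefore not a justification.

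**The case against.** The best defence is that this is a small descriptive study, that nobody intends to run a test, and that the word significant is used loosely. The per-subject table supports part of this. A reader might infer that positive reactions could disappear from the report; the documents do not support that, because section 14 promises every subject's responses and section 7 classifies each site. Only the product-level conclusion is undefined. But if the study is descriptive, the significance wording has no function and should go.

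A second defence is that n=20 may come from a sound calculation that was badly summarised. That is possible. A reader might infer that 20 is an arithmetic error or too few. The documents do not show this: an SD near 2.1 to 2.3 mm would give 20, and nothing in them makes that SD implausible. Another route is to take 1.35 as a standardised effect in a two-arm comparison at two-sided 1% and 95% power: 2 × (2.576 + 1.645)² / 1.35² ≈ 19.5, so 20 per arm. That needs a power that is not stated and two arms that the trial does not have.

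A reader might also take 1.35 as percentage points and conclude that 20 falls far short. No percent sign is attached to the 1.35 and no expected rate is given, so that reading is conjecture and carries no weight here.

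Finally, the 99% level is not tied to a positive rate, and 20 is the minimum number of completers. For that reason the limits are shown at two levels and for both 20 and 30 subjects.

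**Conclusion.** The reporting rule is wrong as written: section 14 excludes analysis and then depends on significance, with nothing elsewhere to resolve the conflict. What is lost is a defined product conclusion, not the individual data.

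The sample size is unsupported, not shown to be wrong. That finding rests only on the absence of inputs; the SDs in the working are what the plan would have had to assume on a mm reading.

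The argument from no expected effect fails whichever reading is taken. The limits assume independent subjects and a binary positive-or-not outcome, and they describe only people who pass section 5.2, which excludes known fish allergy among other things. This should be fixed before data are seen. It does not call for a different number of subjects.

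**What to change.** Amend section 14 as follows.

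- **Analysis sentence.** Say that there will be no hypothesis test, and that results will be given as counts with exact confidence limits only.
- **Reporting rule.** Remove the reference to significance. Report the number of subjects positive to the test product at any reading (primary summary) and at each of T1, T2 and T3, over the number evaluable. Give the exact one-sided upper limit at one level fixed before data are seen (95% or 99%, for the sponsor to choose). The product conclusion quotes the any-reading count and its limit, and says that it applies to subjects screened under section 5.2. Define evaluable in the same place, starting from the existing control criterion.
- **Withdrawn reactors.** A subject who meets the control criterion and is positive at any reading counts as positive in the any-reading summary, even if later withdrawn. Section 10 keeps data after discontinuation only where the reason was related to the product, so it needs a matching exception.
- **Sample size.** Delete the power sentence and the sentence arguing from no anticipated effect, and state the precision that 20 to 30 subjects give. The alternative is for the sponsor to supply the original calculation with endpoint, unit, SD or rate, sidedness and width. Any other reason for 20 completers is for the sponsor to state; the documents give none.
- **Threshold.** Before any count, reconcile the two definitions of a positive wheal: at least 3 mm (section 7 and section 9.6, and in line with the grading in Table 1) and more than 3 mm (section 7).

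The cost is a written amendment with IRB submission under section 12 and a few lines in the report. Enrolment and visits do not change. The downside for the sponsor is that the stated precision will look less favourable than the present wording suggests.

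### Section 14 rules out statistical analysis yet bases the product conclusion on statistical significance, and no rule leads from positive subjects to a product statement

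*Combined protocol and SAP*

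**What the plan says.** Section 14 (Statistical rationale and data reporting) makes these statements in order:

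- On sample size: "Our power analysis calculation indicates at a confidence level of 99% and confidence interval of 1.35, we will need a sample size of n=20".
- On analysis: "No statistical analysis will be performed".
- On expectation: "No significant effect or interaction effects are anticipated hence the small sample size".
- On presentation: "Skin responses to the test product and controls for each subject will be presented in a table in the final report".
- On the product conclusion, opening the next paragraph: "Product reporting for skin sensitization will be based on statistically significant positive scores at each interval".

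The intervals are the readings at 15 minutes (T1), 6 hours (T2) and 24-48 hours (T3).

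Section 7 has a rule for a single site: a wheal at the cut-off "in response to the test product with expected reactions to both the positive and negative controls, the site will be considered a positive allergen". Sections 7 and 9.6 use the controls to decide whether a test is valid: "The wheal at the positive control must exceed a wheal at the negative control by 3 mm" and "Both controls must show correct reaction in order to proceed with study".

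About 30 subjects are to be enrolled so that 20 complete. The sole objective (Section 2) is the sensitization potential of the product.

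**The concern.** Significance cannot be established without an analysis, so obeying one sentence of Section 14 breaks the other. The significance sentence is also the only place where the plan says how subject-level results become a statement about the product, and it lacks every element needed to run it. The phrase about each interval is itself open: it could mean a separate statement at each reading, or a requirement met at all three.

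If positives occur, two analysts with the same table could report different product conclusions, and the protocol could not show which of them had followed the plan. The design has no randomization or blinding and a single objective, so a conclusion rule fixed in advance matters.

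**Working it through.** **1. Can the plan's own figure supply the missing test?** The 99% and the 1.35 stand in the sample-size sentence. The precision formula for one mean is n = (z × SD / h)², with z = 2.5758 at 99%. The documents give no SD, so n=20 cannot be reproduced. It can only be solved backwards, assuming 1.35 is in mm:

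- half-width 1.35: SD = 1.35 × √20 / 2.5758 = 2.34 mm
- full width 1.35, so h = 0.675: SD = 0.675 × √20 / 2.5758 = 1.17 mm

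Either way this concerns the precision of an estimate. It names no test, comparator or null rate, and the 99% is not stated as the level of a test.

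**2. Can another section supply it?** The controls decide whether a subject's test is valid (Sections 7 and 9.6) and are not stated as a comparator. The Section 7 cut-off classifies one site in one subject and does not say how many positive subjects bear on the product.

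**3. Does the missing choice matter?** The tests and null rates below are assumptions for illustration; none comes from the documents. Take n = 20 with k positive subjects.

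- One-sample binomial, one-sided: p = P(X ≥ k), X ~ Bin(20, p0).
- Exact paired (McNemar) test, with no subject positive at the negative control: 0.5^k one-sided, 2 × 0.5^k two-sided (capped at 1).

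| k | p0 = 1% | p0 = 5% | p0 = 10% | paired, one-sided | paired, two-sided |
|---|---|---|---|---|---|
| 0 | 1 | 1 | 1 | 1 | 1 |
| 1 | 0.182 | 0.642 | 0.878 | 0.50 | 1 |
| 2 | 0.017 | 0.264 | 0.608 | 0.25 | 0.50 |
| 3 | 0.001 | 0.075 | 0.323 | 0.125 | 0.25 |
| 4 | <0.0001 | 0.016 | 0.133 | 0.0625 | 0.125 |
| 5 | <0.0001 | 0.0026 | 0.043 | 0.031 | 0.0625 |

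At 0.05:

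- With k = 0, no test for an excess is significant.
- The 5% null and the paired test agree (not significant) at k = 1 to 3 and diverge at k = 4.
- Divergence at k = 2 or 3 needs a lower null rate, such as 1%. A null rate of 0.1% would make even one positive significant (p = 1 − 0.999^20 = 0.020).

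Borrowing the 99% as a 1% level does not settle the matter: 5 of 20 gives 0.0026 against a 5% null but 0.031 or 0.0625 in the paired test.

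**4. What would a descriptive report show?** Clopper-Pearson two-sided 95% limits: for k = 0 the upper limit is 1 − 0.025^(1/n), which is 16.8% for 0/20 and 11.6% for 0/30. For 1/20 the interval is 0.1% to 24.9%; for 4/20 it is 5.7% to 43.7%.

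**The case against.** The most favourable reading is that the significance wording is loose language for scores that meet the wheal cut-off. The same section disclaims analysis and promises a per-subject table, and Section 7 defines positivity by wheal size. On that reading the two sentences no longer conflict. The text does not say this, however, and the reading still leaves no step from positive subjects to a product statement. The objection tempers the contradiction but does not remove the gap.

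It can also be said that little turns on it. The plan expects no significant effect and excludes known fish allergy, so zero positives is plausible, and then no test on the positive/negative classification would find an excess. That stands, within a limit: wheal diameters are also recorded, and a test on diameters could differ even if no wheal reaches the cut-off.

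A reader might infer two stronger things. One is that positive reactions could be concealed behind a non-significant result. The documents do not support that, because Section 14 tabulates every subject's responses. The other is that any small number of positives produces conflicting conclusions. That does not follow either: the 5% null and the paired test agree up to 3 of 20, and earlier conflict rests on a lower null rate that no document states.

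Finally, exact intervals and an any-time-point count go beyond the smallest repair, which is to delete or define one sentence. That is fair, but deletion alone would leave the product statement without a rule.

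**Conclusion.** The point holds. Read literally, the two sentences of Section 14 cannot both be followed. On the loose reading there is still no rule for a product statement. This rests on the text and needs no number.

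The practical effect depends on the outcome. On the positive/negative classification there is none with zero positives. With positives, the product conclusion can turn on a test chosen after the data are seen, as 4 of 20 shows (p=0.016 against 0.0625). The p-values assume the tests and null rates named; the paired ones also assume that no subject is positive only at the negative control. One such subject moves the two-sided value at k = 4 from 0.125 to 2 × 6/32 = 0.375. They illustrate the gap and do not bound it.

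The defect is confined to the product-level conclusion. It should be corrected before the first reading, because this is the plan's only group-level rule.

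**What to change.** In Section 14, delete the significance sentence and replace the statement that there will be no analysis with a descriptive rule along these lines:

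> For each of T1, T2 and T3, the number and percentage of subjects with a positive test site will be reported with an exact (Clopper-Pearson) 95% confidence interval. The number positive at any time point will also be reported, each subject counted once. The product result will be stated as positive reactions in k of n subjects or, if there are none, as no positive reactions observed in n subjects, with the exact upper limit. No significance test will be used to classify the product.

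State the denominator. For each time point: subjects who met the protocol's control criterion at the first reading and were evaluated at that time point. For the any-time-point count: all such subjects with at least one reading, with every observed positive counted and listed, including in subjects who later discontinue. Two passages make this necessary. Section 9.6 describes the control check only at the first reading. Section 10 leaves out discontinued subjects' data unless the discontinuation was product-related, and must be reconciled with the new rule.

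Separately, so that the count is defined, reconcile the cut-off. Section 7 uses both at least 3 mm and strictly more than 3 mm, Section 9.6 uses at least 3 mm, and Table 1 grades 3 mm as +1.

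The cost is one paragraph in Section 14, reconciled wording in Sections 7 and 10, and a few exact intervals, with no new data. The downside is a less reassuring statement when positives are few or absent: the upper limit is 16.8% for 0/20, 11.6% for 0/30 and 24.9% for 1/20.
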